3.3.6 Dose intensity

Dose intensity will be derived for study treatment durvalumab or placebo. Relative dose intensity (RDI) is the percentage of the actual dose intensity delivered relative to the intended dose intensity through to treatment discontinuation.

RDI will be defined as follows:

- $RDI = 100\% * d/D$, where d is the actual cumulative dose delivered up the actual last day of dosing and D is the intended cumulative dose up to the actual last day of dosing. D is the total dose that would be delivered, if there were no modification to dose or schedule. When accounting for the calculation of intended cumulative dose 3 days should be added to the date of last dose to reflect the CSP allowed window for dosing.

When deriving actual dose administered the volume before and after infusion will also be considered.

Example of dose intensity for durvalumab (MEDI4736)

RDI	Patient	Study day									
		1	29	57	85	113	141	169	197	225	
100%	1	X	X	X	X	X	X	X	X	X	PD
100%	2	X	X	X	X	X	X	X	X[D]		PD
56%	3	X	X	X	O	X	X				PD

X: Dose of 1500g taken; O: Dose missed; [D] Dose discontinued; PD: Progressive disease

Patients 1-3 progressed on Day 230, so the intended dose through to progression was 9 * 1500mg of durvalumab = 13500mg (13.5g).

Patient 1 received a total of 13.5g of durvalumab, whereas other patients received less treatment due to:

- Early stopping prior to PD (Patient 2)
- Dosing delays (Patient 3)

The Patient 2 example illustrates that for RDI, the end of actual dosing period is calculated based on the smallest recovery period after the last non-zero dose.

Patient 1: $RDI = (9 * 1.5g) / 13.5g = 100\%$

Patient 2: $RDI = (8 * 1.5g) / 12g = 100\%$

Patient 3: $RDI = (5 * 1.5g) / 13.5g = 56\%$

3.3.7 Concomitant Medication

Any medications taken by the patient at any time between the date of the first dose (including the date of the first dose) of study treatment up to the date of last dose of study treatment in the study will be considered as concomitant medication. Any medication that started prior to the first dose of the study treatment and ended after the first dose or is ongoing will be considered as both prior and concomitant medication.

Allowed and disallowed concomitant medications will be presented by ATC classification and generic term.

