6.4 Concomitant therapy

The Investigator must be informed as soon as possible about any medication taken from the time of part II screening until the end of the clinical treatment phase of the study including the 90-day safety Follow-up Period following the last dose of study drug.

Any medication or vaccine including over-the-counter or prescription medicines, vitamins, and/or herbal supplements that the participant is receiving at the time of enrolment or receives during the study must be recorded along with:

• Reason for use

- Dates of administration including start and end dates
- Dosage information including dose, unit, and frequency

Participants must be instructed not to take any medications, including over-the-counter products, without first consulting with the Investigator.

Restricted, prohibited, and permitted concomitant medications are described in the following tables (Table 5 and Table 6). Refer also to the Dosing Modification and Toxicity Management Guidelines (see Section 8.4.5).

Prohibited medication/class of drug:	Usage:	
For all treatment arms		
Any investigational anticancer therapy other than those under investigation in this study	Should not be given concomitantly whilst the participant is on study treatment	
mAbs against CTLA-4, PD-1, or PD-L1 other than those under investigation in this study	Should not be given concomitantly whilst the participant is on study treatment	
Any concurrent chemotherapy, radiotherapy, immunotherapy, or biologic, or hormonal therapy for cancer treatment other than those under investigation in this study	Should not be given concomitantly whilst the participant is on study treatment. (Concurrent use of hormones for non-cancer-related conditions [eg, insulin for diabetes and hormone replacement therapy] is acceptable.	
Live attenuated vaccines	Should not be given through 30 days after the last dose of IP	
Immunosuppressive medications including, but not limited to, systemic corticosteroids at doses exceeding 10 mg/day of prednisone or equivalent, methotrexate, azathioprine, and tumour necrosis factor- α blockers	 Should not be given concomitantly, or used for premedication prior to the study treatment infusions. The following are allowed exceptions: Use of immunosuppressive medications for the 	
	 management of study treatment-related AEs Short-term premedication for participants receiving SoC CRT, in which the prescribing information or local guidance for the agent 	

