3.3 Safety variables

Safety and tolerability will be assessed in terms of AEs (including serious AEs [SAEs]), deaths, laboratory data, vital signs, electrocardiograms (ECGs) and exposure. These will be collected for all patients.

Unless otherwise specified, ‘on-treatment’ will be defined as assessments between date of the first dose and 90 days following last dose of the IP (durvalumab/placebo) or initiation of the first subsequent anti-cancer therapy (excluding palliative radiotherapy), whichever occurs first.

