Pneumonitis, Hepatic events, Diarrhea/Colitis, Intestinal perforations, Adrenal Insufficiency, Type 1 diabetes mellitus, Hyperthyroid events, Hypophysitis, Hypothyroid events, Thyroiditis, Renal events, Dermatitis/Rash, Pancreatic events, Myocarditis, Myasthenia gravis, Guillain-Barre syndrome, Myositis, Infusion/hypersensitivity reactions, Other rare/miscellaneous. Other categories may be added or existing terms may be merged as necessary. An AstraZeneca medically qualified expert after consultation with the Global Patient Safety Physician has reviewed the AEs of interest and identified which preferred terms contribute to each AESI/AEPI. A further review will take place prior to Database lock (DBL) to ensure any further terms not already included are captured within the categories.

Immune-mediated Adverse Events (imAEs)

imAEs will be identified from both AEs of special interest (AESIs) and AEs of possible interest (AEPIs) based on programmatic rules that consider interventions involving systemic steroid therapy, immunosuppressant use, and/or endocrine therapy (which, in the case of AEPIs, occurs after first considering an Investigator’s causality assessment and/or an

Investigator's designation of an event as immune-mediated). Endocrine therapies include standard endocrine supplementation, as well as treatment of symptoms resulting from endocrine disorders (for example, therapies for hyperthyroidism include beta blockers [e.g., propranolol], calcium channel blockers [e.g., verapamil, diltiazem], methimazole, propylthiouracil, and sodium perchlorate). Further details are provided in the imAE charter.

In addition, the Sponsor may perform medical review of those AESIs and classify them as imAEs or not imAEs via an independent manual adjudication process.

Confirmed/Suspected COVID-19 infection

Confirmed/suspected COVID-19 infection is defined as an AE with preferred term within the AE search criteria developed by the latest MedDRA MSSO guidance for COVID-19.

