4.2.5.1 Adverse events

All AEs, both in terms of current MedDRA PT and CTCAE grade, will be summarised descriptively by count (n) and percentage (%) for each treatment group. Any AE occurring before randomised treatment (i.e. before the administration of the first infusion on Study Day 1) will be included in the AE listings, but will not be included in the summary tables (unless otherwise stated). These will be referred to as 'pre-treatment'. However, any AE occurring before the administration of the first dose on Study Day 1 that increases in severity after the first dose will be regarded as treatment emergent and thus will be included in the majority of summary tables.

A treatment emergent AE (TEAE) is an AE with an onset date (and time, if applicable) following the first dose of study treatment, or a pre-existing AE which worsens following the first dose of study treatment through to 90 days after the last dose of study treatment (i.e., the last dose of durvalumab/placebo).

AEs observed up until 90 days following discontinuation of the study treatment (i.e., the last dose of randomised treatment) or until the initiation of the first subsequent anti-cancer therapy (excluding palliative radiotherapy) following discontinuation of study treatment (whichever occurs first) will be used for reporting of all the AE summary tables. For all IDMC and interim analyses (IAs) deliveries, this will take into account the earliest date from: AEs observed up until 90 days following discontinuation of the study treatment, initiation date of the first subsequent anti-cancer therapy (excluding palliative radiotherapy) or the data cut-off (DCO) date applicable to that delivery.

This will more accurately depict AEs attributable to study treatment only as some of AEs up to 90 days following discontinuation of the study treatment are likely to be attributable to subsequent therapy.

However, to assess the longer-term toxicity profile, some of the AE summaries will also be produced containing AEs observed up until 90 days following discontinuation of the study treatment (i.e. without taking subsequent therapy into account)

Any events in this period that occur after a patient has received further therapy for cancer (following discontinuation of study treatment) will be flagged in the data listings.

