 - AE onset prior to subsequent therapy. Which includes AEs with an onset date (or pre-treatment AEs that increase in severity) on or after the date of first dose and up to and including 90 days following the last dose of study medication (durvalumab/placebo), or AE start date \leq the date of initiation of the first subsequent therapy (whichever occurs first).
- Death after end of safety follow up period (last dose of study medication (durvalumab/placebo) + 90 days) and not due to disease under investigation
- COVID-19 related death
- Unknown reason for death
- Other deaths

This summary will be repeated for all deaths on-treatment or within 90 days of last dose of durvalumab/placebo.

Adverse events of special interest and possible interest

Preferred terms used to identify adverse events of special interest and possible interest (as defined in [section 3.3.1](#)) will be listed before DBL and documented in the Study Master File. Grouped summary tables of certain MedDRA preferred terms will be produced and may also show the individual preferred terms which constitute each AESI/AEPI grouping. Groupings will be based on preferred terms provided by the medical team prior to DBL, and a listing of the preferred terms in each grouping will be provided.

An overall summary will include the number and percentage of patients with:

- Any AESI/AEPI (*)
- Any AESI/AEPI, causally related to durvalumab/placebo (*)
- Any AESI/AEPI of CTCAE grade 3 or 4
- Any AESI/AEPI of CTCAE grade 3 or 4, causally related to durvalumab/placebo
- Any AESI/AEPI with outcome of death
- Any AESI/AEPI with outcome of death, causally related to durvalumab/placebo

- Any serious AESI/AEPI (*)
- Any serious AESI/AEPI, causally related to durvalumab/placebo
- Any AESI/AEPI leading to discontinuation of durvalumab/placebo (*)
- Any AESI/AEPI leading to discontinuation of durvalumab/placebo, causally related to durvalumab/placebo
- Any AESI/AEPI leading to dose delay of durvalumab/placebo
- Any AESI/AEPI leading to concomitant medication (*)
- Any AESI/AEPI leading to concomitant medication use (steroids) (*)
- Any AESI/AEPI leading to concomitant medication use (high dose steroids) (*)
- Any AESI/AEPI leading to concomitant medication use (endocrine therapy) (*)
- Any AESI/AEPI leading to concomitant medication use (other immunosuppressants) (*)

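### The SAP closes the concomitant-medication window at the last infusion, but AESI/AEPI reporting runs up to 90 days longer, so treated-event rows and the disallowed-medication table can miss treatment started in that gap

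*SAP*

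**What the plan says.** SAP 3.3.7 holds the SAP's only definition of concomitant medication. Medication taken from the first dose "up to the date of last dose of study treatment in the study will be considered as concomitant medication". One carry-over clause follows: "Any medication that started prior to the first dose of the study treatment and ended after the first dose or is ongoing" counts as both prior and concomitant. Nothing covers a drug first started after the last dose. The section then says that allowed and disallowed concomitant medications will be tabulated by ATC class and generic name.

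The neighbouring windows are longer:

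- SAP 3.3 defines on-treatment as "assessments between date of the first dose and 90 days following last dose of the IP (durvalumab/placebo"), or to first subsequent anti-cancer therapy if earlier.
- SAP 4.2.5.1 bases the AE tables on "AEs observed up until 90 days following discontinuation of the study treatment", with the same earlier cut. Some tables are repeated without that cut.
- Protocol 6.4 collects medication from part II screening to the end of the treatment phase, "including the 90-day safety Follow-up Period following the last dose of study drug".

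The AESI/AEPI overview in SAP 4.2.5.1 includes rows such as "Any AESI/AEPI leading to concomitant medication use (steroids"), with parallel rows for high dose steroids, endocrine therapy and other immunosuppressants. These rows are starred, so they are repeated by group term and preferred term. A second AESI/AEPI summary in the same section has rows for systemic corticosteroids, high dose steroids and other immunosuppressants that do not use the term concomitant medication. SAP 3.3.1 identifies imAEs through "programmatic rules that consider interventions involving systemic steroid therapy, immunosuppressant use, and/or endocrine therapy" and leaves the details to an imAE charter.

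**The concern.** Infusions are every 4 weeks, and an immune event that ends treatment may well arise between two of them. In such a patient the last dose is the infusion before the event, so the steroid, immunosuppressant or hormone replacement given for it starts after the 3.3.7 window has closed. The event is inside the AE window and its treatment is outside the medication window. The same applies to late-onset events first treated in the 90-day follow-up.

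At stake is the description of how much AESI/AEPI needed treatment. The overview rows could come out too low, and could disagree with the second summary, which asks nearly the same question without the defined term. The endocrine row has no counterpart in that second summary, so a shortfall there would not show up by comparison. Separately, a disallowed-medication table that stops at the last dose cannot show breaches of a prohibition that continues after it.

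**Working it through.** The documents give no figure for this point, so the check is date arithmetic followed by a rough sizing.

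**Windows for one patient.** Inputs: 28-day dosing interval; total exposure ending at last dose + 27 days, absent death or data cut-off (SAP 3.3.5.1); AE window ending at last dose + 90 days (SAP 4.2.5.1). Take a last infusion on Day 113, an AESI on Day 127 treated with a steroid that day, no further study drug and no subsequent therapy.

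| Quantity | Formula | Day |
|---|---|---|
| End of medication window (3.3.7) | 113 + 0 | 113 |
| End of exposure | 113 + 27 | 140 |
| Next infusion due | 113 + 28 | 141 |
| End of AE window | 113 + 90 | 203 |

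The AESI on Day 127 is counted, since 127 ≤ 203. The steroid is not concomitant, since 127 > 113. SAP 3.3.5.1 supports this reading: when treatment is stopped between cycles, the last recorded administration is the date used. The medication window therefore closes before the SAP's own exposure period does.

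**Size of the gap.** 203 − 113 = 90 days at most, and less where subsequent therapy starts and the table applies that cut. For a patient with a single infusion, the medication window is 1 day and the AE window at most 1 + 90 = 91 days.

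**What still qualifies.** A drug started by the last infusion date and continued was taken within the window. A drug with an incomplete or missing date is presumed concomitant under the imputation rules in SAP 4.1.4.

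**Disallowed medication.** Protocol Table 5 bars live attenuated vaccines through 30 days after last dose. A vaccine on Day 123 (113 + 10) falls within that period, which runs to Day 143 (113 + 30), but outside a 3.3.7 window ending on Day 113.

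**Rough number of patients.** Inputs: about 400 randomised 2:1 (SAP 1.3); 5% to 10% discontinuing for an AE in earlier monotherapy studies (protocol 2.3.2.1).

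- Durvalumab arm: 400 × 2/3 ≈ 267.
- Stopping for an AE: 267 × 0.05 ≈ 13 to 267 × 0.10 ≈ 27.
- The share of these that are AESI/AEPI first treated after the last infusion is not given. Assuming 25% to 100%: 13.3 × 0.25 ≈ 3, up to about 27.

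This covers only patients who stop for an AE. Late events in patients who stop for other reasons are not in it. The count actually lost is 0 if the programming links events to all recorded medication.

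**The case against.** The strongest reply is that 3.3.7 may never have been meant to govern the AESI and imAE derivations. The only output it names is the ATC tabulation, which the SAP places with study-population summaries on the mITT and ITT sets, whereas AE tables use the safety analysis set. Neither SAP 3.3.1 nor 4.2.5.1 refers back to it. The imAE rule speaks of interventions, and its matching rules sit in a charter that is not among the documents. A row about an event leading to a treatment describes a link rather than a calendar window, and data for that link are collected: treatment given for each AE (protocol 8.3.4) and a reason for use for each medication (protocol 6.4). Most Table 5 prohibitions apply only while the patient is on treatment, so ending the general medication table at last dose is defensible.

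Much of this stands, and it rules out stronger readings. A reader might infer that treated immune toxicity is undercounted, that AESIs are lost, or that the difference between arms is diluted. The documents do not support these. AESI/AEPI are identified by preferred term, so an event that ends treatment still appears in the any-event and discontinuation rows, and in the serious, grade 3 or 4 and fatal rows where it qualifies. No figure shows that affected events concentrate in the durvalumab arm; that is an inference from mechanism.

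The reply does not remove the problem. The overview rows use a term that the SAP defines once, and the SAP nowhere says that they draw on anything wider. The presumption in 4.1.4 serves incomplete dates; a fully dated start after the last dose is clearly outside. The AE treatment field is listed without drug class or dose, so on its face it cannot fill the high dose or endocrine rows. Sponsor review of AESIs is optional.

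**Conclusion.** The windows are inconsistent, and a stated rule followed literally gives wrong rows. The overview AESI/AEPI rows tied to concomitant medication would omit treatment first started after the last infusion, over a gap of up to 90 days, and could disagree with the parallel rows in the second summary. The disallowed-medication table would miss post-dose live vaccines within the 30-day prohibition.

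imAE classification is affected only if the charter or the programming draws on the 3.3.7 subset. The number of treated events lost is not established: about 3 to 27 durvalumab patients on the assumptions above, and possibly 0. The finding rests on the wording of the SAP, not on evidence of how the tables were programmed. It should be corrected because the change is small and removes a real ambiguity in the safety tables.

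**What to change.** In SAP 3.3.7 or 4.2.5.1, state that treated-AESI/AEPI rows and imAE derivations use all medication recorded from first dose to 90 days after last dose, ending at first subsequent anti-cancer therapy wherever the matching AE table applies that cut. Confirm that the imAE charter uses the same window. Extend the disallowed-medication summary to cover the protocol's post-dose prohibition period. The general allowed-medication ATC table can stay at last dose, so no study-wide redefinition is needed.

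The cost is a sentence or two in the SAP and a changed date bound in programming. Protocol 6.4 already provides for collecting the data. Reported treated-AESI/AEPI rates may be slightly less favourable.

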3.4 Pharmacokinetic and Immunogenicity Variables

Analyses to evaluate the pharmacokinetics (PK) and immunogenicity of durvalumab will be performed by AstraZeneca/MedImmune Clinical Pharmacology group or designee. Only the

earliest available test result will be used for analysis if multiple tests are performed for one sample.

3.4.1 Pharmacokinetic analysis

Individual durvalumab concentrations will be listed by visit. Summary statistics of durvalumab concentrations will be calculated and tabulated by visit. Individual and mean blood concentration-time profiles will be generated. The following PK parameters will be determined after the first and steady-state doses: peak concentration and trough concentration (as data allow). Samples below the lower limit of quantification (LLOQ) will be treated as missing in the analyses. If the data are suitable, the relationship between PK exposure and efficacy/safety parameters may be investigated graphically or using an appropriate data modelling approach, which will not be included in the CSR of this study.

3.4.2 Immunogenicity analysis

Serum samples for anti-drug antibody (ADA) assessments will be conducted utilising a tiered approach (screen, confirm, titer), and ADA data will be collected at scheduled visits shown in the CSP. ADA result from each sample will be reported as either positive or negative. If the sample is positive, the ADA titer will be reported as well. In addition, the presence of neutralising antibody (nAb) may be tested for all ADA-positive samples using a ligand-binding assay. The nAb results will be reported as positive or negative.

The number of patients in the ADA analysis set who fulfil the following criteria will be determined. The percentage of ADA-positive patients in each of the category will be calculated, using the number of patients in the ADA analysis set of the treatment group as the denominator. A patient is defined as being ADA positive if a positive ADA result is available at any time, including baseline and all post-baseline measurements; otherwise ADA negative.

- ADA positive at any visit; the percentage of ADA-positive patients in the ADA analysis set is known as ADA prevalence.
- Treatment emergent ADA positive: the sum of both treatment-induced and treatment-boosted ADA; the percentage of patients fulfilling this criterion in the ADA analysis set is known as ADA incidence.
- ADA positive post-baseline and positive at baseline.
- ADA positive post-baseline and not detected at baseline (treatment-induced ADA).
- ADA not detected post-baseline and positive at baseline.
- Treatment-boosted ADA, defined as a baseline positive ADA titer that was boosted to a 4-fold or higher level (greater than the analytical variance of the assay) following drug administration.

- Persistently positive ADA, defined as having at least 2 post-baseline ADA positive measurements with at least 16 weeks (112 days) between the first and last positive measurement or an ADA positive result at the last available assessment. The category includes patients meeting these criteria who are ADA positive at baseline.
- Transiently positive ADA, defined as having at least one post-baseline ADA positive measurement and not fulfilling the conditions for persistently positive. The category includes patients meeting these criteria who are ADA positive at baseline.
- nAb positive at any visit.

Immunogenicity results will be analysed descriptively by summarising the number and percentage of patients who develop detectable ADAs against durvalumab. The immunogenicity titre and presence of neutralising ADAs will be reported for samples confirmed positive for the presence of ADAs. The effect of immunogenicity on PK, pharmacodynamics, efficacy, and safety will be evaluated, if the data allow.

